2. OVERVIEW (SYNOPSIS)

Sponsor: PROMOMED RUS LLC, Russia	Separate study table relating to part of the dossier	(For use by national authorized bodies only)
Name of finished product: Areplivir, film-coated tablets	Volume: Pages:	
Active ingredient: Favipiravir		
Protocol No.: FAV052020		
Clinical study name: Open randomized multicenter comparative study on the efficacy and safety of Areplivir film-coated tablets (PROMOMED RUS LLC, Russia) in patients hospitalized with COVID-19		
Investigators, Study site: The study is conducted at five research centers in the Russian Federation. Detailed information is provided in Section 6.		
Publication: A list of scientific papers and publications relevant to this study will be presented in the Clinical Study Final Report.		
Study period: Q2 2020 – Q4 2020	Drug development phase: III	
Study purpose: Assess the efficacy and safety of Areplivir versus standard therapy in patients hospitalized with COVID-19. Study objectives: 
 • Assess the efficacy of Areplivir versus standard therapy in patients hospitalized with COVID-19. • Assess the safety of Areplivir versus standard therapy in patients hospitalized with COVID-19. 		
Methodology: an open randomized multicenter comparative study on the efficacy and safety of Areplivir in patients hospitalized with COVID-19.		
Number of patients (planned and included in the analysis): The study will randomize 200 patients. Given the possible non-inclusion of patients at the screening stage, the maximum number of patients to sign the Informed Consent Form in the Patient Information Leaflet and to participate in screening can be no more than 210 people. This interim report is based on data on 80 patients (40 patients in the Areplivir arm + 40 patients in the standard therapy arm). Patients who met the inclusion criteria and did not meet the non-inclusion criteria were randomized to 2 groups (treatment arms) in a 1:1 ratio: Arm 1 (n=100) receives the study drug Areplivir film-coated tablets: on day 1 of therapy - 1600 mg (8 tablets) 2 times a day; on days 2-14 of treatment - 600 mg (3 tablets) 2 times a day. The drug is taken orally every 12 hours, swallowing whole tablet without chewing and washing down with a glass of water. The course of treatment is 14 days.		

Sponsor: PROMOMED RUS LLC, Russia	Separate study table relating to part of the dossier	(For use by national authorized bodies only)

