
Statistical methods:
 
Justification of sample size
 
The study will randomize 200 patients. Given the possible non-inclusion of patients at the screening stage, the maximum number of patients to sign the Informed Consent Form in the Patient Information Leaflet and to participate in screening will be no more than 210 people.
 
At the first stage, 40 patients are included in each study arm and the most sensitive efficacy criterion of the two selected is determined, or additional analysis is carried out to select the criterion from secondary ones. Given 40 patients in each of the study arms, the sensitivity of the study to confirm 15% superiority by incidence, supposing the expected response 80% in the test drug arm, will exceed 45%.
 
Two Independent Proportions (Null Case) Power
 
Analysis
 
Numeric Results of Tests Based on the Difference: P1 - P2 H0: P1 - P2 ≥ 0. H1: P1 - P2 = D1 < 0. Test Statistic: Z test with pooled variance
 
  
 	Sample Size Grp 1	Sample Size Grp 2	Prop H1 Grp 1 or Trtmnt P1	Prop Grp 2 or Control P2	Diff if H0 D0	Diff if H1 D1	Target Alpha	Actu Alpha	
   
 Power	0.4553	40	40	0.6500	0.8000	0.0000	-0.1500	0.0500	0.0500	
  
				Sample Size Grp 1	Sample Size Grp 2	Prop H1 Grp 1 or Trtmnt P1	Prop Grp 2 or Control P2	Diff if H0 D0	Diff if H1 D1	Target Alpha	Actu Alpha	Power	0.4553	40	40	0.6500	0.8000	0.0000	-0.1500	0.0500	0.0500
	Sample Size Grp 1	Sample Size Grp 2	Prop H1 Grp 1 or Trtmnt P1	Prop Grp 2 or Control P2	Diff if H0 D0	Diff if H1 D1	Target Alpha	Actu Alpha													
Power	0.4553	40	40	0.6500	0.8000	0.0000	-0.1500	0.0500	0.0500												

Sponsor: PROMOMED RUS LLC, Russia	Separate study table relating to part of the dossier	(For use by national authorized bodies only)
Name of finished product: Areplivir, film-coated tablets	Volume: Pages:	
Active ingredient: Favipiravir		

Said statistical power (45%) is acceptable for exploratory stages of the studies aimed to select the duration for endpoint monitoring and to select the endpoint at the second (confirming) stage.

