In case change of the planned endpoints, separate adjustment will be made for the multiplicity of comparisons and the required number will be recalculated at the second stage.

The total planned number of patients before the completion of the first stage will be 100 patients in each of the arms.

The estimated calculation until the data of the first stage are obtained is as follows. Given the available data from Chinese researchers, 15% superiority of favipiravir therapy over standard therapy without favipiravir is allowed in relation to the rate of improvement by 2 or more categories on categorical scale by day 10 of treatment. The adopted higher response to standard therapy of 70% is associated with a longer duration relative to the Chinese study (10 days instead of 7 days).

An RCT enrolling patients within 12 days of symptom onset found that favipiravir was superior to arbidol in terms of the clinical recovery rate at day 7 in patients with mild illness (62 [56%] of 111 with arbidol vs 70 [71%] of 98 with favipiravir), but not in those with critical illness (0 vs 1 [6%]). (Chen C. Huang J. Cheng Z. et al. Favipiravir versus arbidol for COVID-19: a randomized clinical trial. medRxiv. 2020; (published online April 15.) (preprint).

Tests for Two Proportions

Numeric Results for Testing Two Proportions using the Z-Test with Unpooled Variance

H0: $P_1 - P_2 \geq 0$ vs. H1: $P_1 - P_2 = D_1 < 0$.

Target	Actual	Diff						
Power	Power*	N1	N2	N	P1	P2	D1	Alpha
0.80170	107	107	214	0.6500	0.8000	-0.1500	0.0500	0.80

* Power was computed using the normal approximation method.

Thus, the minimum number of subjects required for a clinical study is 200 with 100 subjects randomized to each of the two groups.

Statistical analysis

The purpose of statistical analysis is to prove superiority of Areplivir, film-coated tablets (PROMOMED RUS LLC, Russia), over standard therapy in patients hospitalized with COVID-19.

The results of statistical analysis, descriptive statistics and illustrative tables, graphs, lists will be presented in interim and final clinical study reports.

General methods of analysis

Statistical analysis is carried out in accordance with the requirements of the Guideline for Good Clinical Practice (ICH 9) approved by the Eurasian Economic Commission, and other applicable requirements and laws.

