
Certified statistical software with validated algorithms is used to perform statistical analyses and to ensure proper documenting (StatSoft Statistica 10.0., IBM SPSS Statistics 22).
 
Descriptive statistics are provided for all efficacy and safety indicators collected during the study. Continuous (quantitative) data are presented using the number of observations, arithmetic mean value, confidence interval (CI) 95% for mean, standard (rms) deviation, median, interquartile span (25th and 75th centiles), minimum and maximum.
 
Ordinal, categorical and qualitative data are presented as absolute frequencies (number of observations), relative frequencies (percent) and 95% CI (unless otherwise stated).
 
The check for normality of distribution is carried out by one of the generally accepted methods (Shapiro-Wilk test, Kolmogorov-Smirnov test). For non-Gaussian distributions, non-parametric methods will be used to compare efficacy and safety indicators.
 
Significance levels and confidence intervals are calculated as bilateral, the statistical significance of differences is two-sided by default and refers to significance level 0.05 (unless specified otherwise).
 
Analysis of demographics and other source data
 
Demographic data (age, sex) and baseline condition data are presented along with summaries in the form of absolute frequencies (number of observations), relative frequencies (percent), or using the arithmetic mean, confidence interval (CI) 95% for mean, standard deviation, median, interquartile span (25th and 75th centiles), minimum and maximum, depending on the type of variable.
 
To test the study group homogeneity hypothesis, at the baseline zero hypotheses (no differences between groups) are tested with Student's t-test (for interval measures with normal distribution in the study population), Mann-Whitney's test (for ordinary measures or for interval measures with distribution different from normal) or Fisher's exact test and χ^2 test (for qualitative indicators). If statistically significant differences between study arms are found, the magnitude of differences is estimated using confidence intervals.
 
Analysis of primary efficacy parameter
 
Primary efficacy endpoints:
 
One of the primary efficacy parameters is the time (in days) to improvement of patient's clinical status according to the categorical ordinal scale of clinical improvement.
 
 • Time (in days) to improvement in clinical status on a categorical ordinal scale of clinical improvement. 
To compare the primary efficacy indicator between arms, the Student's t-test for independent samples is used. If the necessary assumptions about the normality of distribution of this indicator are not met, the non-parametric Mann-Whitney test will be used. Also, the Kaplan-Meier technique and compilation survival tables can be used as descriptive methods for studying this efficiency parameter. Gehan-Wilcoxon test, Cox-Mentel test or Log-Rank test can be used to compare the time (in days) to improve the clinical status of the patient between the study groups.
		

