
Sponsor: PROMOMED RUS LLC, Russia	Separate study table relating to part of the dossier	(For use by national authorized bodies only)
Name of finished product: Areplivir, film-coated tablets	Volume: Pages:	
Active ingredient: Favipiravir		

The proof of the superiority hypothesis is the establishment of a statistically significant time difference (in days) before patient's clinical status improvement between the Areplivir arm and the standard therapy arm.

The next primary efficacy parameter is the percentage of patients who achieved an improvement in clinical status according to the categorical ordinal scale of clinical improvement by 2 or more categories at Visit 3.

- Rate of clinical status improvement by categorical ordinal scale of clinical status improvement by 2 or more categories at Visit 3.

For the analysis of this parameter, an intergroup comparison of percentages is used using a two-sided version of the **Fischer's exact test** (or a two-sided version of the χ^2 (chi-square) test, if all the expected values in the cells of the contingency table for this analysis are 5 or more). The percentage of patients who achieved improvement in clinical status on a categorical ordinal clinical improvement scale by 2 or more categories at Visit 3 is presented with a two-sided 95% confidence interval by treatment arm. Hypothesis testing is performed at a 5% significance level. The difference in proportion between treatment arms and the 95% bilateral confidence interval for the difference in proportion calculated by **Newcomb-Wilson technique is presented**.

The proof of the hypothesis of superiority of Areplivir film-coated tablets (PROMOMED RUS LLC, Russia) is the establishment of a statistically significant difference in the proportions of patients who achieved an improvement in clinical status according to the categorical ordinal scale of clinical improvement by 2 or more categories at Visit 3, between Areplivir arm and standard therapy arm.

Analysis of the primary efficacy parameter is performed in the ITT population (main analysis), and in the PP population (additional analysis). A summary of all efficacy indicators is provided.

Analysis of secondary efficacy parameters

The following efficacy parameters in the protocol are represented by qualitative values:

- Percentage of patients with elimination * COVID-19 according to PCR analysis at Visit 3.
- Percentage of patients transferred to intensive care unit.

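### The primary Visit 3 responder test is valid but unadjusted; a prespecified adjustment for baseline category and age, already collected, would add a modest amount of power at little cost

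*Combined protocol and SAP*

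**What the plan says.** All references are to the Combined protocol and SAP, section 2, Overview (Synopsis).

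- *Analysis of primary efficacy parameter.* One of the two primary criteria is the proportion improving by at least two scale categories at Visit 3. The test is described as: "For the analysis of this parameter, an intergroup comparison of percentages is used using a two-sided version of the" Fisher exact test, replaced by chi-square if every expected cell count is at least 5. A Newcombe-Wilson interval for the difference in proportions accompanies it. "Hypothesis testing is performed at a 5% significance level".
- *General methods.* "the statistical significance of differences is two-sided by default and refers to significance level 0.05".
- *Analysis of demographics and other source data.* "Demographic data (age, sex) and baseline condition data are presented along with summaries". The arms are then compared at baseline with significance tests. Where a difference is significant, its size is described by confidence intervals. Nothing carries it into the efficacy comparison.
- *Key inclusion criteria.* Temperature, breathing rate, SpO2, CRP and lung CT are needed to establish the medium severity form.
- *Study site.* "The study is conducted at five research centers in the Russian Federation".

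No covariate-adjusted or stratified efficacy analysis is described for any endpoint.

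**The concern.** The endpoint is a change from the baseline scale category, so that category must be on record for every patient who can be scored. Age is recorded too. Both could plausibly predict response by day 10, and the plan uses them only to describe the arms and to test whether they differ. Prognostic information already paid for is therefore left out of the primary comparison.

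This matters more than usual because the trial has little power to spare. Under the planned two-sided test with 100 per arm, power for 65% vs 80% is about 66%, not 80%. A chance imbalance of some size is also likely. Assuming simple randomisation, the probability that the arms differ by more than 0.2 SD on a given baseline variable is about 16% at 100 per arm and 37% at 40 per arm. If a baseline test comes out significant, the plan gives no rule for what follows, which leaves room for an adjustment chosen after the fact.

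**Working it through.** **Inputs from the plan.** Rates of 65% and 80%, a difference of 0.15 and alpha 0.05, from the power table ("0.6500 0.8000 0.0000 -0.1500 0.0500"). The stage 1 table has a directional hypothesis ("H0: P1 - P2 ≥ 0. H1: P1 - P2 = D1 < 0. Test Statistic: Z test with pooled variance"). Planned size is 100 per arm, and the analysis is two-sided at 0.05.

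**Input assumed.** R², the share of outcome variance explained by the baseline covariates. The documents give no value.

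**1. Reproduce the plan's figures.** Unpooled Z-test, one-sided, 107 per arm:

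- SE = √[(0.65×0.35 + 0.80×0.20)/107] = √(0.3875/107) = 0.0602
- Power = Φ(0.15/0.0602 − 1.645) = Φ(0.848) = 0.8017, as stated.

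At 40 per arm, one-sided, the result is 0.4425 pooled or 0.4519 unpooled, against 0.4553 stated. That is close enough to confirm the one-sided basis; two-sided, the values are 0.321 and 0.331.

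**2. Power of the planned two-sided test at 100 per arm.** The mean rate is 0.725, so about 27.5 non-responders are expected per arm and chi-square applies, not Fisher.

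- SE under H0 = √(2×0.725×0.275/100) = 0.0631
- SE under H1 = √(0.3875/100) = 0.0622
- Power = Φ[(0.15 − 1.960×0.0631)/0.0622] = Φ(0.421) = 66.3% (67.3% unpooled).

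**3. Effect of adjustment.** Adjustment reduces the variance of the risk difference by about the factor (1 − R²), so the effective size per arm is 100/(1 − R²).

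| Assumed R² | Effective n per arm | Two-sided power | N per arm for 80% |
|---|---|---|---|
| 0 | 100 | 66.3% | 138 |
| 0.05 | 105.3 | 68.6% | 132 |
| 0.10 | 111.1 | 70.9% | 125 |
| 0.15 | 117.6 | 73.4% | 118 |
| 0.20 | 125 | 76.0% | 111 |
| 0.30 | 142.9 | 81.4% | 97 |

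The sample-size text adopts a different control rate ("The adopted higher response to standard therapy of 70% is associated with a longer duration"). With 70% vs 85%, power is 72.2% unadjusted and 74.4% to 79.1% for R² 0.05 to 0.15, so the gain is again about 2 to 7 points.

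**4. Check by simulation.** 100 per arm, 65% vs 80%, one normally distributed baseline score, 4,000 trials per setting (Monte Carlo standard error about 0.75 points):

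| Log-odds per SD | Approx. R² | Chi-square | Adjusted logistic | Adjusted, under H0 |
|---|---|---|---|---|
| 0 | 0 | 67.2% | 66.9% | 4.6% |
| 0.5 | 0.045 | 66.9% | 68.8% | 4.6% |
| 1.0 | 0.15 | 67.6% | 74.4% | 4.8% |
| 1.5 | 0.26 | 66.1% | 77.7% | 4.7% |

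A setting closer to the proposed model uses a two-level baseline category plus age, of modest to moderate assumed strength. It gave about 66% unadjusted and 67% to 70% adjusted.

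**5. Standard error of the standardised risk difference.** With an uncorrected influence-function standard error and the category-plus-age model, rejection under H0 was 5.2% to 5.8% at 100 per arm and 5.7% to 6.9% at 40. In a separate run that added centre, it was 6.3% and 8.1%. A small-sample correction, or a logistic Wald test, brought it to about 5% at 100 per arm and 4.4% to 5.9% at 40.

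**The case against.** The strongest reply is that this is a preference. The chi-square test with a Newcombe-Wilson interval is prespecified and valid, and it targets the same marginal difference that the trial was sized on. That stands: the point concerns efficiency, not an error. A reader might also infer that chance imbalance biases the unadjusted test. It does not, because the test's type I error already allows for such imbalance.

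The second reply is that the gain may be small, and this largely stands. Only the medium severity form is enrolled and patients needing intensive care are excluded, which narrows the baseline range. The ordinal scale is not reproduced in the documents, and most patients may start in one category. A reader could infer a gain of more than 10 points, as in the bottom row of the simulation, but that needs log-odds of 1.5 per SD, which nothing in the documents supports.

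The third reply is that changing a primary analysis in an open-label trial with stage 1 data on 80 patients already reported invites a charge of data-driven choice. That also stands. It governs how the change is made; it does not make adjustment wrong.

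Finally, one might extend the advice to stratifying a log-rank or Cox analysis of time to improvement. The plan does not support that. Its named comparison is a t-test or Mann-Whitney test, log-rank is only optional, and no Cox regression is planned.

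**Conclusion.** The point holds as a recommended improvement. The primary Visit 3 comparison is valid but leaves out the baseline category and age, both already collected. With R² assumed at 0.05 to 0.15, adjustment raises two-sided power at 100 per arm from about 66% by roughly 2 to 7 points, and a category-plus-age model may sit in the lower half of that range. If the covariates carry no prognostic value, nothing material is lost. The direction holds for any R² above zero; the size rests wholly on the assumed R².

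A reader might infer that adjustment would restore the intended 80% power. It would do so only at R² near 0.30, well above the cautious range. The main shortfall comes from sizing one-sided at 107 per arm and testing two-sided at 100 per arm, which is a separate matter to be settled on its own.

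**What to change.** Amend *Analysis of primary efficacy parameter* for the Visit 3 responder rate:

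- **Primary analysis.** Logistic regression of response on treatment, baseline ordinal category and age. Predict each patient's response probability under each arm, average over all patients and take the difference. Report this marginal risk difference with a 95% CI and a two-sided 5% test, using a small-sample-corrected or bootstrap standard error. The estimand stays a difference in proportions.
- **Covariates.** Leave centre out. State in advance how sparse baseline categories are merged.
- **Supportive analysis.** Keep the chi-square or Fisher test with the Newcombe-Wilson interval.
- **Timing.** Fix the covariates on prior grounds before the confirmatory outcome data are analysed. Record the change as a plan amendment that says what was known from the 80 stage 1 patients at that time. If those patients count towards the 200, say so, since part of the confirmatory data has then already been reported.

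The cost is slightly more programming and a documented amendment, with no extra patients or data.

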
Diagnosis and key inclusion criteria:
 
The study is conducted with the participation of male and female patients aged 18 to 80 years inclusive, hospitalized with COVID-19.
 
Inclusion criteria:
 
 1. Signing and dating of the Informed Consent Form of the Patient Information Leaflet (PIL) by patients. 2. Men and women aged 18 to 80 years inclusive at the time of signing the Informed Consent Form in PIL. 3. No difficulty with oral medication (e.g. swallowing disorder). 4. Patient diagnosed with "Coronavirus infection caused by SARS-CoV-2 (confirmed)¹, medium severity form*" established in accordance with the Interim Guidelines of the Russian Ministry of Health for the prevention, diagnosis and treatment of a new coronavirus infection (COVID-19), (revision 6 of 28.04.2020). *Medium severity form: fever above 38 °C, BR above 22/min, dyspnea during exercise, pneumonia (confirmed by lung CT), SpO2 < 95%, CRP serum level above 10 mg/l. 5. Patient should be hospitalized no more than 48 hours before the start of the study therapy. 6. Positive PCR result for presence of SARS-CoV-2 RNA at screening phase (results obtained within 7 days prior to screening are appropriate). 7. Patient's consent to use reliable contraceptive methods throughout the study and within 1 month for women and 3 months for men after its completion. Persons eligible for participation in the study: 
 – Women who have a negative pregnancy test and use the following contraceptives: barrier method (condom or occlusive cap (diaphragm or cervical/vaulted cap)) or double barrier method of contraception (condom or occlusive cap (diaphragm or cervical/vaulted cap) plus spermicide (foam/gel/film/cream/suppository)). Women incapable of childbearing may also participate in the study 		

¹ Positive PCR result for SARS-CoV-2 RNA.

Sponsor: PROMOMED RUS LLC, Russia	Separate study table relating to part of the dossier	(For use by national authorized bodies only)
Name of finished product: Areplivir, film-coated tablets	Volume: Pages:	
Active ingredient: Favipiravir		

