- Percentage of cases with non-invasive lung ventilation.
- Percentage of cases with mechanical lung ventilation.
- Incidence of fatal cases.
- Assessment of lung injury according to CT data at Visits 4, 5 and 6.**

* Virus elimination is defined as two negative laboratory tests for SARS-CoV-2 RNA obtained at intervals of 24 hours.

**An "empirical" visual scale will be used to estimate changes in lung involvement from CT data.

For the analysis of these parameters, an intergroup comparison of shares is used using a two-sided version of the **Fischer's exact test** (or a two-sided version of the χ^2 (chi-square) test, if all the expected values in the cells of the contingency table for this analysis are 5 or more).

The protocol also includes the following endpoint:

- Time (in days) to fever disappearance (body temperature < 37.2 ° C for 3 consecutive days

Sponsor: PROMOMED RUS LLC, Russia	Separate study table relating to part of the dossier	(For use by national authorized bodies only)
Name of finished product: Areplivir, film-coated tablets	Volume: Pages:	
Active ingredient: Favipiravir		

without antipyretic medication).

For the secondary efficacy parameter "time (in days) to fever disappearance (body temperature < 37.2 °C for 3 consecutive days without antipyretic drugs), a comparison between arms is made using the *Student's t-test* or the *Mann-Whitney test* (depending on the nature of the distribution of quantitative indicators). Also, *Kaplan-Meier technique* and the construction of *survival tables* can be used as descriptive methods of study. The *Gehan-Wilcoxon test, the Cox-Mentel test or the Log-Rank test* can be used to compare the time (in days) to the disappearance of fever in the study arms.

Analysis of secondary efficacy parameters is performed in the ITT population (main analysis), and in the PP population (additional analysis).

In case of developing acute respiratory distress syndrome and the need to switch patient to mechanical ventilation, the investigational drug is canceled, but the patient is not withdrawn from the study. Patients are under follow-up until Visit 6, the data are taken into account to assess efficacy in the ITT population.

Safety Analysis

Safety criteria

Safety assessment includes the following parameters:

- Total number of adverse events (AEs) stratified by severity and incidence;
- Incidence of adverse drug reactions;

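### The CT lung outcome is tested as shares by Fisher or chi-square, which makes no use of category order; a rank-based test would gain power if the scale is graded

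*Combined protocol and SAP*

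**What the plan says.** All references are to the Overview (Synopsis) of the combined protocol and SAP.

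- **Endpoint.** Under secondary efficacy criteria the plan lists "Assessment of lung injury according to CT data at Visits 4, 5 and 6".
- **Data type.** The analysis of secondary efficacy parameters opens its list with "The following efficacy parameters in the protocol are represented by qualitative values". CT stands on that list beside viral elimination, ICU transfer, ventilation and death.
- **Scale.** A footnote says that an empirical "visual scale will be used to estimate changes in lung involvement from CT data". It gives no categories, no cut-off and no reference scan.
- **Test.** "For the analysis of these parameters, an intergroup comparison of shares is used using a two-sided version of the" Fisher exact test, or of chi-square when every expected cell count is at least 5. No ordinal test and no baseline covariate is named for CT.
- **Elsewhere.** The general methods say: "For non-Gaussian distributions, non-parametric methods will be used to compare efficacy and safety indicators". For baseline homogeneity, Mann-Whitney is assigned "for ordinary measures or for interval measures with distribution different from normal" (the first term apparently means ordinal), and Fisher or chi-square to qualitative indicators.
- **Baseline CT.** Inclusion criterion 4 includes CT-confirmed pneumonia in its definition of medium severity, and patients who cannot undergo CT are not included. A baseline scan should therefore exist.

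**The concern.** The other items on the list are yes/no events. A visual reading of lung involvement is more naturally graded, from better to worse. Fisher and chi-square return the same p-value however the grades are reordered, so a consistent shift towards better grades gets no credit for being consistent. Splitting the scale in two restores a direction but discards the information within each half.

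The plan draws the distinction between ordinal and qualitative data itself when it compares the arms at baseline, but does not carry it over to this outcome.

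What is at stake is efficiency on the only imaging endpoint. It matters somewhat more than for an ordinary secondary, because the sample-size section allows additional analysis after stage 1, on 40 patients per arm, to pick a criterion from the secondary ones. An insensitive test makes CT look less responsive than it may be.

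**Working it through.** **No CT figure to reproduce.** The plan gives no power, effect size or category distribution for CT. Its two power tables concern the binary primary endpoint (65% against 80%) and do not bear on this point.

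**Inputs from the plan.** Two-sided alpha 0.05; 1:1 allocation; 100 per arm in total and 40 per arm at stage 1.

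**Assumed inputs.** Ordered grades, best first, with these control distributions: A, five even grades (20% each); B, 10/40/30/15/5%; C, four grades, 15/45/30/10%; D, 15/35/30/15/5%. The treatment effect is a common odds ratio (OR) on every cumulative split: logit(treated cumulative share) = logit(control cumulative share) + ln(OR).

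**Example, distribution C, OR 2.0.** The control cumulative shares 0.15, 0.60, 0.90 have odds 0.1765, 1.5, 9. Doubled, these are 0.353, 3, 18, which give treated cumulative shares 0.261, 0.750, 0.947. Treated shares are therefore 26.1/48.9/19.7/5.3%.

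**Simulated power, 100 per arm, OR 2.0** (3,000 trials per cell for A to C, 4,000 for D; split after the second-best grade; Monte Carlo standard error at most √(0.5 × 0.5/3000) = 0.9 points):

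| Control distribution | Chi-square, all grades | Two-way split | Mann-Whitney | Loss, all grades | Loss, split |
|---|---|---|---|---|---|
| A | 58.0% | 68.8% | 78.2% | 20.2 | 9.4 |
| B | 53.1% | 66.7% | 74.9% | 21.8 | 8.2 |
| C | 56.3% | 61.2% | 73.8% | 17.5 | 12.6 |
| D | 55% | 68% | 77% | 22 | 9 |

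**Closed-form check of the split in C** (60% against 75%). The pooled SE is √(2 × 0.675 × 0.325/100) = 0.0662 and the unpooled SE is √((0.24 + 0.1875)/100) = 0.0654. Power is Φ((0.15 − 1.96 × 0.0662)/0.0654) = Φ(0.31) = 62%, in line with the simulated 61.2%.

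**Fewer grades.** With as few as three assumed grades the all-grade chi-square does better. Over three to five grades it has 55-63% power against 74-77% for Mann-Whitney. The smallest gap is about 10 points, which sets the lower end of the 10 to 22 range.

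**Other effects and sizes, A to C** (all grades / split / Mann-Whitney):

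- 100 per arm, OR 1.5: 20-22% / 28-32% / 34-36%.
- 100 per arm, OR 2.5: 81-83% / 84-89% / 93-95%.
- 40 per arm, OR 2.0: 20-23% / 28-36% / 37-41%.
- OR 1.0: every test rejects in about 4-6% of trials.

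**Does the plan's test rule apply?** Chi-square needs all expected counts to be at least 5. In B and D the worst grade holds 5% of controls. At OR 2.0 the treated share is 1 − 38/39 = 2.6%, so the expected count is 100 × (0.050 + 0.026)/2 = 3.8, and Fisher would usually apply (in 78% of trials under D). In C the smallest expected count is 100 × (0.100 + 0.053)/2 = 7.6. In A it is 100 × (0.200 + 0.111)/2 = 15.6. Chi-square is thus normally the planned test in A and C, where the all-grade losses are 20.2 and 17.5 points.

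**Baseline adjustment.** None of these simulations contains a baseline variable. As a linear approximation, residual variance falls to 1 − ρ² of its unadjusted value: 0.91, 0.75 or 0.51 for an assumed baseline to follow-up correlation ρ of 0.3, 0.5 or 0.7.

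**The case against.** **A reader might infer that the plan ignores the baseline scan.** The documents do not support that. The footnote says the scale estimates changes, and a change is judged against an earlier scan, so baseline may already be inside the outcome (improved, unchanged or worse, for example). What stands is narrower: the reference scan is not named, and the test does not adjust for baseline CT.

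**The ordering is inferred.** The plan does not say how many categories there are. It speaks of shares and lists CT among yes/no outcomes, so a two-category share is a natural reading. This stands. If the scale itself is two-category there is no loss; if a graded scale is split, the smaller loss applies.

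**The simulations favour the rank test.** A common odds ratio is close to its best case, and with a non-monotone effect it need not win. This stands as a condition on the size. The figure of 100 CTs per arm is also an upper limit, because patients discharged early need not attend Visits 5 and 6.

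**Fisher would often replace chi-square.** This is true in B and D. Fisher on the full table ignores order too, but its power was not computed, so those two rows are only a guide.

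**The general rule on non-parametric methods might cover CT.** It is tied to non-Gaussian distributions, whereas the CT-specific text names only Fisher and chi-square. It does not settle the matter.

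**A change of endpoint brings a multiplicity adjustment and a new sample-size calculation.** That limits the consequence at stage 1, where every option has low power, but it does not change the CT test.

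**Conclusion.** The point holds as a matter of efficiency. The plan's test for CT makes no use of category order, the reference scan is unstated, and baseline CT is not adjusted for.

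At 100 per arm and an assumed common odds ratio of 2.0, the cost against Mann-Whitney is roughly 10 to 22 points of power if all categories are tested and 8 to 13 if they are split in two. This requires three or more ordered categories and a consistent shift. The category distributions and the effect are assumptions, because the documents give neither, and the loss is nil for a two-category scale.

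A reader might go further and infer that the CT comparison is invalid or that the main conclusion is at risk. Neither follows: type I error is held, and CT is a secondary endpoint unless stage 1 changes that. It is a worthwhile improvement rather than a necessary correction.

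**What to change.** 1. State the CT scale's ordered categories, and the scan against which change is judged.
2. For CT, replace Fisher/chi-square with a Mann-Whitney test at each visit. Where the baseline scan is graded on the same scale, use instead a van Elteren test stratified by baseline CT grade, or a proportional-odds model with treatment and baseline CT grade.
3. Keep the share improved, by arm and with its confidence interval, as a supportive summary, and fix the definition of improved in advance.

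The cost is SAP wording and minor programming, plus a check of proportional odds if that model is used; the rank tests do not need it. No new data are required if the baseline scan is graded on the same scale.
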